### 5.6.3 Laboratory Values

Laboratory results will be summarized using Système International (SI) units, as appropriate. For all quantitative parameters listed in [protocol Section 9.5.1.5.3 Safety Assessments \(Laboratory Measurements\)](#), the actual value and the change from baseline to each postbaseline visit and to the end of treatment (defined as the last on-treatment value) will be summarized by visit using descriptive statistics. Qualitative parameters listed in [protocol Section 9.5.1.5.3 Safety Assessments \(Laboratory Measurements\)](#) will be summarized using frequencies (number and percentage of subjects), and changes from baseline to each postbaseline visit and to end of treatment will be reported using shift tables. Percentages will be based on the number of subjects with both nonmissing baseline and relevant postbaseline results.

Laboratory test results will be assigned a low/normal/high (LNH) classification according to whether the value was below (L), within (N), or above (H) the laboratory parameter's reference range. For each laboratory parameter, shift from baseline (LNH) to each postbaseline visit and at the end of treatment will be presented. Similar shift tables from baseline (LNH) to the highest/lowest postbaseline value will also be presented.

[Protocol Appendix 2 \(Sponsor's Grading for Laboratory Values\)](#) presents the criteria that will be used to identify subjects with treatment-emergent markedly abnormal laboratory values (TEMAV). Except for phosphate, a TEMAV was defined as a postbaseline value with an increase from baseline to a grade of 2 or higher. For phosphate, a TEMAV was defined as a postbaseline value with an increase from baseline to a grade of 3 or higher. The number and percentage of subjects with TEMAVs will be presented; each subject will be counted once in the laboratory parameter high and low categories, as applicable. Markedly abnormal laboratory values will be flagged in the subject data listings.

For ALT and AST analysis, the number of subjects with greater than 3 times, but less than 5 times the ULN and the number of subjects with greater than 5 times the ULN will be summarized. For bilirubin, a summary of the number of subjects with serum concentrations greater than 2 times the ULN will be created. These summaries will also be provided for the maximum value in the treatment duration. In addition, the number of subjects who meet the criteria for Hy's Law will be summarized by visit and during the treatment duration. A subject will be determined to have met Hy's Law if AST or ALT is  $> 3x$  ULN, bilirubin  $> 2x$

ULN, and alkaline phosphatase  $\leq 2x$  ULN at a visit. The number of subjects who meet each of the criteria for Hy's Law during treatment (but not all necessarily at the same visit) will also be summarized.

#### 5.6.4 Vital Signs

Descriptive statistics for vital signs parameters (ie, systolic and diastolic BP, pulse, respiratory rate, temperature, weight) and changes from baseline will be presented by visit.

In addition, the criteria described in the table below will be used to determine clinically notable results for blood pressure and heart rate. The number (percentage) of subjects with clinically notable results over all scheduled and unscheduled visits will be summarized.

**Table 1: Criteria for Clinically Notablea Vital Signs**

Variable	Criterion Value	Change Relative to Baseline
Systolic BP	> 180 mmHg	Increase of $\geq 20$ mmHg
	< 90 mmHg	Decrease of $\geq 20$ mmHg
Diastolic BP	>105 mmHg	Increase of $\geq 15$ mmHg
	< 50 mmHg	Decrease of $\geq 15$ mmHg
Heart Rate	>120 bpm	Increase of $\geq 15$ bpm
	< 50 bpm	Decrease of $\geq 15$ bpm
Weight		Increase of > 7%
		Decrease of > 7%

a: Clinically notable means that a value must have met both the criterion value and satisfied the magnitude of change relative to baseline.

The criteria in Table 2 will be used to determine abnormal results for blood pressure and heart rate. The number of subjects with abnormal results will be summarized.

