9.3.1 Inclusion Criteria

Subjects must meet all of the following criteria to be included in this study:

1. Have a diagnosis of epilepsy with POS with or without secondarily generalized seizures or PGTC according to the ILAE Classification of Epileptic Seizures (1981). Diagnosis should have been established at least 6 months prior to Visit 1 by clinical history and an EEG that is consistent with the diagnosis; normal interictal EEGs will be allowed provided that the subject meets the other diagnosis criterion (ie, clinical history).
2. Male or female subject, from age 4 to less than 12 years at the time of informed consent/assent.
3. Have a minimum weight of 16 kg (35 lb).
4. Have had a brain imaging (eg, magnetic resonance imaging [MRI] scan or computed tomography [CT]) before Visit 1 that ruled out a progressive cause of epilepsy.
5. During the 12 weeks \pm 3 days (4 weeks \pm 3 days in Japan only) prior to Visit 2, subjects must have had equal or greater than 1 POS or 1 PGTC seizure. (revised per Amendments 01 and 02) Only simple POS with motor signs, complex POS, and complex POS with secondary generalization are counted toward this inclusion for POS.
6. Are currently being treated with stable doses of 1 to a maximum of 3 approved AEDs. (revised per Amendment 01) Doses must be stable for at least 4 weeks before to Visit 1; in the case where a new AED regimen has been initiated for a subject, the dose must be stable for at least 8 weeks prior to Visit 1. Only 1 EIAED (defined as carbamazepine, phenytoin, oxcarbazepine, or eslicarbazepine) out of the maximum of 3 AEDs is allowed (A vagal nerve stimulator [VNS] will be counted as one of the 3 allowed AEDs). (revised per Amendment 01)

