## 3.2 Overall Study Design and Plan

This was a multicenter, open-label single-arm study in children (ages 4 to <12 years) with inadequately controlled POS or PGTC. The study was to consist of a Core Study and Extension Phase (Extension A, for all countries in the study) with an Additional Extension Phase (Extension B) available for subjects enrolled in Japan only. Subjects were to be stratified by age ( $\geq 4$  to <7 years, 7 to <12 years) with at least 30% subjects enrolled in the equal or greater than 4 to less than 7 year age group for each seizure type (ie, at least 36 with POS and at least 12 with PGTC).

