### Growth parameter

The actual value and change from baseline in growth parameter (height, weight, TSH, fT3, fT4 and IGF-1) will be summarized by visit. Height and weight will present summary statistics for overall percentile and overall z-score.

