**Table 1: Criteria for Clinically Notablea Vital Signs**

Variable	Criterion Value	Change Relative to Baseline
Systolic BP	$> 180$ mmHg	Increase of $\geq 20$ mmHg
	$< 90$ mmHg	Decrease of $\geq 20$ mmHg
Diastolic BP	$> 105$ mmHg	Increase of $\geq 15$ mmHg
	$< 50$ mmHg	Decrease of $\geq 15$ mmHg
Heart Rate	$> 120$ bpm	Increase of $\geq 15$ bpm
	$< 50$ bpm	Decrease of $\geq 15$ bpm
Weight		Increase of $> 7\%$
		Decrease of $> 7\%$
a: Clinically notable means that a value must have met both the criterion value and satisfied the magnitude of change relative to baseline.		

The criteria in [Table 2](#) will be used to determine abnormal results for blood pressure and heart rate. The number of subjects with abnormal results will be summarized.

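### In both SAPs the weight row of the clinically notable vital-signs table cannot be applied as written, and the SBP limit above 180 mmHg would practically never be met at ages 4 to under 12

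*SAP*

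**What the plan says.** Section 5.6.4 of the Core SAP introduces Table 1 with criteria that "will be used to determine clinically notable results for blood pressure and heart rate". The lead-in does not name weight, but the table has a weight row. That row gives only a change from baseline, "Increase of > 7" per cent or the same percentage decrease, and its criterion-value cell is empty. Note a reads: "Clinically notable means that a value must have met both the criterion value and satisfied the magnitude of change relative to baseline". For high systolic pressure the table requires more than 180 mmHg together with a rise of at least 20 mmHg. One set of limits covers every age.

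The Extension SAP (section 5.6.4, Table 1) has the same row, note and lead-in. Its section 8.2.1 keeps the baseline at the last available value before the first Core dose.

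Two other outputs matter here. Table 2 in both SAPs counts changes in systolic pressure of at least 20 and at least 40 mmHg with no absolute limit, and it has no weight row. The growth paragraph of Core SAP section 5.6.6 states "Height and weight will present summary statistics for overall percentile and overall z-score", and the Extension SAP plans the same. No flag is tied to those z-scores.

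**The concern.** Vital signs are part of the primary safety endpoint (section 5.1.1 of both SAPs), so a count headed clinically notable will be read as a safety result. The weight row can be programmed in two ways, and the documents do not choose between them. One way returns zero whatever happens to the children. The other measures a growing child against a fixed pre-treatment weight, so ordinary growth accumulates in the count. The high-SBP row has a different problem: if the limit lies far beyond any value expected at these ages, a count of zero says nothing about the drug.

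**Working it through.** The plan gives no expected count for this table, so there is no figure to reproduce. Growth rates and paediatric blood pressure are not in the documents. Those used below are assumptions, shown as ranges.

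**Reading the weight row**

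- Note a taken literally: there is no criterion value to meet, so no child can be flagged for gain or loss.
- Change alone: any child more than 7% above or below the pre-Core baseline is flagged.

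These are alternatives. Both cannot happen in the same table.

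**Size under the change-alone reading**

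Inputs from the documents: the 7% limit; the 16 kg entry minimum (Protocol 9.3.1); Weeks 23 and 52.

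- 7% in kilograms: 0.07 × 16 = 1.12 kg; 0.07 × 25 = 1.75 kg; 0.07 × 30 = 2.10 kg; 0.07 × 40 = 2.80 kg.
- Annual growth that reaches 7%: 7 / (23/52.18) = 15.9% per year by Week 23; 7 / (52/52.18) = 7.0% per year by Week 52.

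Assume growth of 6–14% per year, with percentage gain normally distributed between children (SD 2–5 points). Mean gain = annual rate × weeks/52.18. Share flagged at one visit = 1 − Φ((7 − mean)/SD).

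| Annual growth | Mean gain, Week 23 | Flagged, Week 23 | Mean gain, Week 52 | Flagged, Week 52 |
|---|---|---|---|---|
| 6% | 2.6% | 1–19% | 6.0% | 30–42% |
| 8% | 3.5% | 4–24% | 8.0% | 58–69% |
| 10% | 4.4% | 10–30% | 10.0% | 72–93% |
| 12% | 5.3% | 20–37% | 12.0% | 84–99% |
| 14% | 6.2% | 34–43% | 14.0% | 92–100% |

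These are single-visit shares. Section 5.6.4 counts subjects across scheduled and unscheduled visits, so the share ever flagged is equal or higher.

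To see which children are affected, assume instead 2–3 kg per year:

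- Week 23: the gain is about 0.88–1.32 kg (2 or 3 × 23/52.18). Dividing by 0.07 gives break-even weights of about 12.6–19 kg. At 2 kg per year no eligible child passes 7%; at 3 kg per year only those under about 19 kg do. A 30 kg child gains 2.9–4.4%.
- Week 52, taken as one year: break-even weights are 2/0.07 = 28.6 kg and 3/0.07 = 42.9 kg.

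**High systolic pressure**

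- From an assumed baseline of 90–110 mmHg, passing 180 needs a rise of more than 180 − 110 = 70 to 180 − 90 = 90 mmHg.
- The 20 mmHg condition adds nothing unless baseline exceeds 180 − 20 = 160 mmHg.
- A 40 mmHg rise, the largest category in Table 2, passes 180 only from a baseline above 180 − 40 = 140 mmHg.
- With an assumed mean of 95–115 mmHg and SD of 8–15 mmHg, 180 lies between (180 − 115)/15 = 4.3 and (180 − 95)/8 = 10.6 SD above the mean. The normal tail probability is at most about 7 in a million per reading.

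**The case against.** The best defence is that Table 1 is a supplementary count in a descriptive single-arm study. No hypothesis, sample size or decision rule depends on it. Table 2 would show a rise in blood pressure even if the high-SBP row were zero. Weight is summarised by visit, percentile and z-score, and both SAPs summarise by age cohort. All of this stands. It limits the information lost, but it does not tell a programmer how to read the weight row or make an unreachable limit informative.

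A reader might infer more than the documents support:

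- That the weight row both fails to fire and misreports growth. Each follows from a different reading.
- That growth swamps the flag in the Core analysis. At Week 23 the assumed mean gain is 2.6–6.2%, below the limit.
- That every child below 29–43 kg is flagged by Week 52. That treats an assumed average of 2–3 kg per year as every child's rate.
- That the high-SBP row is empty by construction. It is empty only given paediatric pressures that the documents do not state, so practically never met is as far as one can go.
- That the whole table fails. Nothing here counts against the diastolic, heart-rate or low-systolic limits.

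**Conclusion.** The concern holds in two parts. First, the weight row is undefined in both SAPs; this follows from the documents alone. Under one reading it never fires. Under the other it largely counts growth by Week 52 (about 30–100% of children, and at least 58% once growth is 8% per year or more), but only a minority by Week 23 (1–43%). The percentages rest on assumed growth of 6–14% per year with an SD of 2–5 points. Second, the SBP limit above 180 mmHg would practically never be met at ages 4 to under 12. This rests on assumed paediatric pressures but is stable across the range tried. The consequence is an uninformative or misleading table within the primary safety reporting; no inference, power or sample size is affected.

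**What to change.** Make the same changes in section 5.6.4 of both SAPs:

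1. Name weight in the lead-in to Table 1 and exempt it from note a.
2. Replace the 7% limits, for gain and for loss, with a change in the weight z-score already planned in section 5.6.6. Pre-specify the cut-off and name the reference standard, which neither SAP does now. A change of 0.5 is only an example and would need its own justification.
3. Replace the high-SBP reporting limit with pre-specified age-appropriate limits, for at least the 4 to <7 and 7 to <12 cohorts.
4. Review the other blood-pressure and heart-rate limits for age and record the reasoning; they may prove adequate.
5. Keep Table 2 as it is.

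The cost is a change to the table text and derivations, with no new data. The downside is that the counts become less comparable with earlier tables.

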**Table 2: Criteria for Abnormal Vital Signs**

Variable	Change Relative to Baseline
Systolic BP	Increase of $\geq 20$ mmHg
	Decrease of $\geq 20$ mmHg
	Increase of $\geq 40$ mmHg
	Decrease of $\geq 40$ mmHg
Diastolic BP	Increase of $\geq 10$ mmHg
	Decrease of $\geq 10$ mmHg
	Increase of $\geq 20$ mmHg
	Decrease of $\geq 20$ mmHg
Pulse	Increase of $\geq 15$ bpm

	Decrease of $\geq 15$ bpm
	Increase of $\geq 30$ bpm
	Decrease of $\geq 30$ bpm

### 5.6.5 Electrocardiograms

ECG parameters (QTcB, QTcF, PR interval, QRS duration and RR interval) and changes from baseline will be presented by visit.

Shift tables will present changes from baseline in ECG interpretation (categorized as normal; abnormal, not clinically significant; and abnormal, clinically significant) to end of treatment.

In addition, the number (percentage) of subjects with at least 1 postbaseline abnormal ECG result in QTc Bazett and QTc Fridericia during the treatment period will be summarized.

Clinically borderline or abnormal ECG results in QTc Bazett and QTc Fridericia will be categorized as follows:

Absolute QTc interval prolongation:

- QTc interval 430-450 ms
- QTc interval  $>450$  ms
- QTc interval  $>500$  ms

Change from baseline in QTc interval:

- QTc interval increases from baseline 30-60 ms
- QTc interval increases from baseline  $>60$  ms.

### 5.6.6 Other Safety Analyses

#### **Aldenkamp-Baker Neuropsychological Assessment Schedule (ABNAS)**

The total ABNAS score (defined as the sum of the individual question scores) and sub-scores for fatigue, slowing, memory, concentration, motor-coordination and language (Brooks et al 2001) will be listed and summarized by visit. Changes from baseline ABNAS sub-scores will be summarized.

**Table 1: Definition between each aspect and question**

Aspect	# of items	Range	Item No
fatigue	5	0-15	1, 7, 13, 18, 24
slowing	5	0-15	2, 8, 14, 19, 23
memory	4	0-12	3, 9, 15, 20
concentration	4	0-12	4, 10, 16, 21
motor speed	3	0-9	5, 11, 17,
reading (language)	3	0-9	6, 12, 22

### Child Behavior Check List (CBCL 1.5/5 and CBCL 6/18)

The CBCL 1.5/5 measures problems in children (1,5 to 5 years old). The data are corrected the problems for children from CRF. To measure problems, 100 ‘problem items’ are rated on a scale to measure their occurrence. Higher scores indicate greater problems, as the scale ranges from 0, indicating ‘not true,’ to 2, indicating ‘often true.’ 67 of the items are then summed into seven syndrome scores (Emotionally Reactive, Anxious/Depressed, Withdrawn, Somatic Complaints, Attention Problems, Aggressive Behavior syndrome and Sleep problems.) The summation of the first four syndrome scores yields the Internalizing Syndrome composite score, and the summation of the next two syndrome scores yields the Externalizing Syndrome composite score. The total problems score is the summation of the two composite scores, the final three syndrome scores, and the 33 ‘problem items’ that were not included in any of the seven syndrome scores.

The total problems score, the Internalizing Syndromes score, the Externalizing Syndromes score, and each of the seven individual syndrome scores of the CBCL 1.5/5 will be evaluated using summaries of change from baseline (Week 0) by visit.

**Table 2: Definition CBCL 1.5-5 (Refer to link of CBCL/1 1/2-5 and LDS in profiles at website <http://www.aseba.org/forms.html>)**

Syndrome scale	#of items	Range	Items
Emotionally Reactive	9	(0-18)	21,46,51,79,82,83,92,97,99
Anxious/Depressed	8	(0-16)	10,33,37,43,47,68,87,90
Withdrawn	8	(0-16)	2,4,23,62,67,70,71,98
Somatic Complaints	11	(0-22)	1,7,12,19,24,39,45,52,78,86,93
Internalizing	36	(0-72)	sum of 4 previous scores
Attention Problems	5	(0-10)	5,6,56,59,95
Aggressive Behavior syndrome	19	(0-38)	8,15,16,18,20,27,29,35,40,42,44,53,58,66,69,81,85,88,96
Externalizing	24	(0-48)	sum of 2 previous scores
Sleep problems	7	(0-14)	22,38,48,64,74,84,94
Total	100	(0-200)	Sum of all problem items scores, including: Internalizing Syndromes, Externalizing Syndromes, Sleep problems, and 33 not yet accounted for problems

Also the CBCL 6/18 measures competencies and problems in children (6 to 18 years old) . To assess competence, sixteen items are scored for each child, with higher scores indicating better competence. The summed scores are grouped into three sub-scores for competence in

activities, social realms and school. The total competence score is the summation of all 16 items.

To measure problems, 120 ‘problem items’ are rated on a scale to measure their occurrence. Higher scores indicate greater problems, as the scale ranges from 0, indicating ‘not true,’ to 2, indicating ‘often true.’ 103 of the items are then summed into eight syndrome scores (Anxious/Depressed, Withdrawn/Depressed, Somatic Complaints, Rule-Breaking Behavior, Aggressive Behavior, Social Problems, Thought Problems, and Attention Problems.) The summation of the first three syndrome scores yields the Internalizing Syndrome composite score, and the summation of the next two syndrome scores yields the Externalizing Syndrome composite score. The total problems score is the summation of the two composite scores, the final three syndrome scores, and the 17 ‘problem items’ that were not included in any of the eight syndrome scores.

The total competence score, the three sub-scores for competence, the total problems score, the Internalizing Syndromes score, the Externalizing Syndromes score, and each of the eight individual syndrome scores of the CBCL 6/18 will be evaluated using summaries of change from baseline (Week 0) by visit.

**Table 3: Definition CBCL 6-18 (Refer to link of CBCL/6-18 scored using three different societies in profiles at website : <http://www.aseba.org/forms.html>)**

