#### **Child Behavior Check List (CBCL 1.5/5 and CBCL 6/18)**

The CBCL 1.5/5 measures problems in children (1.5 to 5 years old). To measure problems, 100 ‘problem items’ are rated on a scale to measure their occurrence. Higher scores indicate greater problems, as the scale ranges from 0, indicating ‘not true,’ to 2, indicating ‘often true.’ 67 of the items are then summed into seven syndrome scores (Emotionally Reactive, Anxious/Depressed, Withdrawn, Somatic Complaints, Attention Problems, Aggressive Behavior syndrome and Sleep problems.) The summation of the first four syndrome scores yields the Internalizing Syndrome composite score, and the summation of the next two syndrome scores yields the Externalizing Syndrome composite score. The total problems score is the summation of all 100 item scores. .

The total problems score, the Internalizing Syndromes score, the Externalizing Syndromes score, and each of the seven individual syndrome scores of the CBCL 1.5/5 will be evaluated using summaries of change from baseline (Week 0) by visit.

**Table 4: Definition CBCL 1.5-5 (Refer to link of CBCL/1 1/2-5 and LDS in profiles at website <http://www.aseba.org/forms.html>)**

Syndrome scale	#of items	Range	Items
Emotionally Reactive	9	(0-18)	21,46,51,79,82,83,92,97,99
Anxious/Depressed	8	(0-16)	10,33,37,43,47,68,87,90
Withdrawn	8	(0-16)	2,4,23,62,67,70,71,98
Somatic Complaints	11	(0-22)	1,7,12,19,24,39,45,52,78,86,93
Internalizing	36	(0-72)	sum of 4 previous scores
Attention Problems	5	(0-10)	5,6,56,59,95
Aggressive Behavior syndrome	19	(0-38)	8,15,16,18,20,27,29,35,40,42,44,53,58,66,69,81,85,88,96
Externalizing	24	(0-48)	sum of 2 previous scores
Sleep problems	7	(0-14)	22,38,48,64,74,84,94
Total	100	(0-200)	Sum of all problem items scores

Also the CBCL 6/18 measures competencies and problems in children (6 to 18 years old). To assess competence, sixteen items are scored for each child, with higher scores indicating better competence. The summed scores are grouped into three sub-scores for competence in activities, social realms and school. The total competence score is the summation of all 16 items.

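### Core SAP 5.6.6 gives two conflicting rules for the CBCL 1.5-5 total problems score: the prose counts 124 items (maximum 248), its own table 100 (0-200)

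*SAP*

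**What the plan says.** Core SAP section 5.6.6, under the Child Behavior Check List, describes the form for younger children. It states that "100 ‘problem items’ are rated on a scale to measure their occurrence", that "the scale ranges from 0, indicating ‘not true,’ to 2, indicating ‘often true", and that "67 of the items are then summed into seven syndrome scores". The list of seven begins with Emotionally Reactive, Anxious/Depressed, Withdrawn and Somatic Complaints and ends with "Attention Problems, Aggressive Behavior syndrome and Sleep problems".

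The composites follow the order of that list. "The summation of the first four syndrome scores yields the Internalizing Syndrome composite score", and the next two, Attention Problems and Aggressive Behavior, make up Externalizing. The total problems score is then described as "the summation of the two composite scores, the final three syndrome scores" together with the 33 items that belong to no syndrome scale.

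The table below this text, Table 2 (Definition CBCL 1.5-5), gives the Total row as 100 items with range 0-200, made up of "Internalizing Syndromes, Externalizing Syndromes, Sleep problems, and 33 not yet accounted for problems". Section 5.6.6 of the Extension SAP defines the same score differently from the Core prose: "The total problems score is the summation of all 100 item scores".

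**The concern.** With seven syndrome scores and six already used in the composites, only Sleep problems is left over. The prose nevertheless adds three more. The last three in the list are Attention Problems, Aggressive Behavior and Sleep problems, and the first two of these are already inside Externalizing. Taken literally, the prose adds Externalizing twice and contradicts the table beneath it.

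The sentence is a scoring rule for a reported outcome. Change from baseline in CBCL at Weeks 23 and 52 is part of secondary endpoint 3. Section 5.6.6 also commits to summarizing change from baseline in the total problems score by visit, and to classifying CBCL results as normal, borderline clinical or clinical from T-scores.

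The Extension SAP bases its analyses on Core and Extension data together (section 5) and uses the same pre-first-dose baseline (section 8.2.1). Two rules for one score could therefore give the same child two baseline totals in two reports.

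**Working it through.** **Inputs.** Item counts from Core SAP Table 2 (Definition CBCL 1.5-5), with at most 2 points per item:

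| Scale | Items |
|---|---|
| Emotionally Reactive | 9 |
| Anxious/Depressed | 8 |
| Withdrawn | 8 |
| Somatic Complaints | 11 |
| Attention Problems | 5 |
| Aggressive Behavior | 19 |
| Sleep problems | 7 |

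The seven item lists hold 67 distinct item numbers with no overlap, so 100 − 67 = 33 items lie outside them. This matches the text.

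**Step 1: composites.**
- Internalizing = 9 + 8 + 8 + 11 = 36 items (0-72)
- Externalizing = 5 + 19 = 24 items (0-48)

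Both agree with the table.

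**Step 2: the table's total.** Internalizing + Externalizing + Sleep + others = 36 + 24 + 7 + 33 = 100 items, maximum 2 × 100 = 200. The stated figure is reproduced exactly.

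**Step 3: the prose total.** Internalizing + Externalizing + (Attention + Aggressive + Sleep) + others = 36 + 24 + (5 + 19 + 7) + 33 = 124 items, maximum 2 × 124 = 248.

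**Step 4: size of the discrepancy.** The excess is 124 − 100 = 24 items, or 248 − 200 = 48 points at most. Since Attention + Aggressive = Externalizing, for any child:

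- prose total = table total + Externalizing
- change in prose total = change in table total + change in Externalizing

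For example, a rise of 5 points on Aggressive Behavior alone raises the table total by 5 and the prose total by 10.

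**Step 5: when the prose total would leave the scale.** It exceeds 200 only if the true total plus Externalizing exceeds 200. Externalizing cannot exceed 48, so the true total must be above 200 − 48 = 152.

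**Step 6: the same wording on the other form.** CBCL 6-18 has eight syndromes. Three form Internalizing (13 + 8 + 11 = 32 items) and two form Externalizing (17 + 18 = 35), so three really are left over (11 + 15 + 10 = 36). The total is 32 + 35 + 36 + 17 = 120 items, maximum 240, as tabulated. The wording works there and fails only on the seven-syndrome form. It may have been carried across from one form to the other, but that is an inference.

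**The case against.** The strongest reply is that the SAP already contains the right answer. Table 2 itemizes every scale and gives the total correctly. The prose itself opens with 100 items and describes the 33 as lying outside all seven scales, so 67 + 33 = 100 can be recovered without any outside source. Core SAP section 9 places the derivation rules in separate documents, and nothing available shows that the faulty sentence was programmed. All of this stands. It makes the point a conflict between two statements, and it makes every consequence conditional on the prose being followed.

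A reader might infer more than the documents support:

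- *Off-scale totals would reach the T-score classification.* Step 5 shows that leaving the scale needs a true total above 152 of 200. Inflation within the scale is the more plausible effect. Section 5.6.6 does not say whether the total is among the scores converted to T-scores, so distortion of the classification is a further conditional.
- *The aggression safety signal would be distorted.* Adverse events of special interest on hostility and aggression are identified through standardized MedDRA queries (section 5.6.2), not through the CBCL. Aggressive Behavior, Attention Problems and Externalizing are each summarized separately, and their definitions are the same under either rule.
- *The effect is broad.* By the form's stated age range (1.5 to 5 years) and the trial's entry ages, the 1.5-5 form applies to the 4- and 5-year-olds. The score is summarized descriptively, and no test or success criterion depends on it.

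What remains is that the Core SAP states two incompatible rules for a reported score and does not say which governs. Its list of changes (section 7) does not mention the CBCL.

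**Conclusion.** The prose rule for the CBCL 1.5-5 total is wrong as written: 124 items and a maximum of 248, against 100 items and 0-200 in the adjacent table and in the Extension SAP. The item counts settle this without any assumption.

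The effect depends on the prose having been programmed in place of the table, which the documents do not show. If it was:

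- each affected total would be too high by that child's Externalizing score, 0 to 48 points;
- changes in Attention Problems and Aggressive Behavior would count twice in the total's change from baseline;
- any T-score classification of the total would be distorted;
- Core and Extension baseline totals for the same child could differ.

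Only the total on this one form is exposed. The syndrome scores, both composites, the 6-18 form, the adverse event summaries and the primary safety endpoint are untouched. It is a contained scoring error in part of a secondary endpoint, worth correcting because the correction is certain and nearly free.

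**What to change.** In Core SAP section 5.6.6, replace the sentence defining the CBCL 1.5-5 total with:

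*The total problems score is the sum of all 100 problem items (Internalizing + Externalizing + Sleep problems + the 33 other items), range 0-200.*

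This agrees with Table 2 and the Extension SAP. The corresponding sentence for CBCL 6-18 should stay as it is.

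Then confirm that the programming specification for the Core analysis uses the 100-item sum. If totals have already been derived, a direct check is whether each one equals Internalizing + Externalizing + Sleep problems + the 33 remaining items.

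The cost is one sentence and one specification check, with no new data and no added analysis.
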